The program evaluation will use mixed methods techniques to assess program acceptability, impact, and effectiveness. Although the goal of the program is to benefit employees, the program evaluation includes measures such as cost-effectiveness, changes in employee absenteeism/presenteeism and qualitative assessments of employee views of the program that will be beneficial to employers using or considering this program for their worksite. In addition, the acceptability and impact of the program will be measured from the perspective of multiple stakeholders – program users, employees at the worksite, and worksite management. Understanding the program outcomes and acceptability from these multiple perspectives will provide rich data for making recommendations for sustaining and disseminating the program.

Although this study will be conducted in India, the results will be applicable to workers in other settings, including the U.S. (see Foreign Justification). Asians, including Asian Indians, are the fastest growing ethnic group in the U.S., and between 2000 and 2010 the Asian Indian population increased by 67.6%.⁷¹ Furthermore, several of the companies committed to this trial (the TATA group, L&T, and Cognizant) have locations worldwide, including offices in America, and these sites would be ideal locations for first phase dissemination. In addition, lessons learned in this study would benefit U.S. companies with worksites in India.

Approach

This study will use a pre-post design at eight diverse worksites to assess program implementation, fidelity, effectiveness, and impact on study participants, workers, and the worksite. There will be no control group because there is already convincing evidence from randomized trials^{8,9,17,53,58,72} that lifestyle intervention is beneficial for preventing diabetes and diabetes-related complications. Although randomized controlled trials provide the most robust evidence for effectiveness, meta-analyses have shown that the results of non-randomized, effectiveness studies do not systematically differ from the results given by randomized controlled trials of the same treatment.^{73,74}

Intervention

The lifestyle intervention will be conducted at eight worksites (see Table 1). These worksites have large workforces (1,500-50,000 employees) and represent a range of industries with locations across India. An overview of activities to be conducted at each worksite are shown in Figure 1.

[figure not shown]

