Preliminary data: D-CLIP [clinicaltrials.gov #NCT01283308, Emory University and Madras Diabetes Research Foundation (MDRF) investigators] is an on-going, translational, diabetes prevention study comparing standard lifestyle advice to a step-wise, culturally tailored program (group lifestyle classes plus metformin for participants not responding to lifestyle change alone) among 602 people with prediabetes in India.²⁵ D-CLIP was developed based on the DPP Curriculum.^{79,80} Early unpublished D-CLIP results are promising. The participation rate for intervention classes was high (83%), and loss to follow-up was low (9%). At eighteen months, lifestyle participants had significantly greater reductions in weight (-1.7 vs. -0.8 kg), BMI (-0.6 vs. -0.3 kg/m²), and waist circumference (-2.7 vs. -2.0 cm) than controls. Additionally, intervention participants showed greater improvements in systolic blood pressure, triglycerides, and HbA_{1c}; 21% of controls achieved improvement in two or more of these risk factors while 33% of intervention group did so. Similar to previous studies showing that weight, BMI, and waist circumference reductions significantly predicted diabetes risk reduction in lifestyle interventions,⁸¹ preliminary D-CLIP analyses show a 51% relative risk reduction in diabetes incidence in intervention participants compared to controls. The effects of the D-CLIP intervention were consistent across sex, age, income, education, and baseline BMI and glucose intolerance.⁸²

Recommendations for improving the Indian diet to better prevent diabetes and reduce cardiometabolic risk factors will be developed based on the work assessing the value of improving food quality of the Global Nutrition and Epidemiologic Transition (GNET) initiative at Harvard University and MDRF. For example, a small crossover trial of substituting brown rice for white rice for five days, found that brown rice lowered glucose levels by 19.8% and fasting insulin by 57%.⁴⁰ GNET studies in other populations further support benefits of improving carbohydrate quality.³⁸ Moreover, studies of acceptability of brown rice in India indicate that well-informed, sensory trained panelists readily accepted brown rice,³² but translating this intervention to the public

Figure 2: Components of the Lifestyle Intervention at the Individual and Worksite Environment Levels

will require additional education and training.²⁷

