Aim 2: Statistical analysis of intervention impact: A generalizing estimating equations (GEE) framework for clustered data⁹⁷ will be used to assess the statistical significance of any observed intervention effect on the endpoints. For the primary endpoint, the dependent variable will be the indicator for whether the study participant is at two or more cardiometabolic risk factor reduction goals at the end of the 3 year follow-up period, minus the expected probability of this endpoint in the absence of an intervention, to be taken as 21% as observed in the D-CLIP²⁵ control group. An exchangeable working correlation matrix will be used to incorporate the clustering within the 8 work-sites, with a log link and binomial variance specified. The exponentiated point and interval estimates from the intercept of this model will quantify the intervention effect, and the p-value associated with the model's intercept will provide a measure of the statistical significance of the findings. A similar GEE approach will be used to estimate and test the significance of intervention effects on secondary endpoints. For continuous markers, such as systolic blood pressure and HbA_{1c}, the post- to pre- within-participant difference will serve as the dependent variable in a GEE model as above, with the identity link function and the distribution specified as normal. The change scores will be evaluated for outliers, and analysis will be repeated with and without extreme outliers. For the cumulative incidence of diabetes at end of follow-up, participants will be coded as one if they satisfy the diabetes definition at end of follow-up and 0 otherwise. A Cox proportional hazards regression model for the diabetes incidence rate will also be considered, and if dropout or loss to follow-up are non-negligible, causal methods for adjusting for dependent censoring will be applied.¹⁰² A similar approach will be used to assess regression to normoglycemia. We will consider worksite-level covariates in multi-level models to examine how these aspects might affect findings. Additional secondary endpoints will be considered (e.g., changes in being at 1, 2 and 3 CVD/T2DM risk factor goals). Although the study is not powered to detect it unless quite large and although no effect modification is expected, we will assess the presence of effect modification by calculating intervention effect estimates stratified by potential modifiers, such as gender, age, marital status, socio-economic status, and assess the statistical significance of any effect modification observed by calculating a cross-product term between the potential modifier and the intervention, using a robust score test to assess the significance of

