Sample Size Selection: This worksite-clustered before-after design of 8 worksites with at least 250 eligible and enrolled participants per site and no more than 20% loss to follow-up (LTF) after 3 years will have 93% or more power to detect an estimated difference between the percent of participants at 2 or more CHD risk factor goals after 3 years of follow-up, the primary effectiveness endpoint of this trial, of 33% or greater, compared to the comparable D-CLIP²⁵ percentage of 21%. The 20% 3-year LTF rate is likely conservative, as only 9% of D-CLIP participants have been lost to follow-up after a mean of 30 months. Similarly, the D-CLIP comparative percentage of 21% is likely conservative, because the D-CLIP control group also experienced a minimal intervention that included meeting with a physician and a dietician, attending two classes (a lecture on diabetes

prevention through weight loss and diet change, and an exercise class), and receiving handouts reinforcing prevention of T2DM. Thus, compared to a community control receiving none of these services, the D-CLIP group would be expected to have a higher percentage at or exceeding two goals, compared to the community standard. In addition, power in this study is excellent for numerous secondary effectiveness endpoints of considerable interest, including 90% power or more to detect a decrease of 2mmHg or greater in systolic blood pressure ($p=0.10$, IIS), 95% power or more to detect a decrease in HbA_{1c} of 0.14% or greater ($p=0.10$, IIS), and nearly 100% power to detect a reduction in diabetes incidence of 30% or greater among the 2/3 of the study participants with prediabetes at baseline screening, compared to the baseline rate of 0.07/year,¹²⁴ otherwise under the same assumptions as the primary endpoint calculation.

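### The primary analysis treats the D-CLIP control rate of 21% as known. Its sampling error is left out, so the interval for the intervention effect is too narrow at any ICC, by an amount the documents do not fix

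*Combined protocol and SAP*

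**What the plan says.** The Approach section sets out a pre-post study at eight worksites: "There will be no control group because there is already convincing evidence" from randomised trials. The comparison therefore comes from outside the trial. Data Analysis, Aim 2 takes the indicator of reaching two or more goals at 3 years and subtracts the probability expected without intervention, "to be taken as 21% as observed in the D-CLIP" control group. The model is a GEE with log link, binomial variance and exchangeable correlation within worksites. The exponentiated intercept and its interval are to quantify the intervention effect, and the intercept's p-value is to give its significance. No term carries uncertainty in the 21%.

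Preliminary data gives the source. D-CLIP was run "among 602 people with prediabetes in India", and "21% of controls achieved improvement in two or more of these risk factors while 33% of intervention group did so". No control-group size, standard error or interval accompanies the 21%.

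Sample Size Selection claims at least 93% power for 33% against 21%, and adds: "Similarly, the D-CLIP comparative percentage of 21% is likely conservative". The reason it gives is that those controls received some services, among them contact with clinical staff and two classes. No ICC is given for the primary endpoint.

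**The concern.** The 21% is an estimate used as a counterfactual. Another D-CLIP control sample would have given a somewhat different percentage, and the estimated program effect would have moved with it one for one. An interval built only from this trial's variance cannot show that.

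Nothing else in the planned primary analysis supplies a no-intervention rate. If the 21% is off by one standard error, the estimated effect shifts by about 2.35 points (301 controls assumed) and the reported interval does not reflect it. The stated power also treats 21% as known.

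**Working it through.** **Inputs**

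- 8 sites x 250 = 2,000 enrolled; 20% loss leaves 1,600, or 200 per site (Sample Size Selection).
- Rates 0.33 and 0.21: difference 0.12; ln(0.33/0.21) = 0.452.
- Alpha 0.05 (Data Analysis). Sidedness is not stated; two-sided with critical value 1.96 is used here.
- D-CLIP control number: not given. Assumption: 301 (half of 602), range 201-401. Losses would lower it: "only 9% of D-CLIP participants have been lost to follow-up after a mean of 30 months", and 0.91 x 301 = 274.
- Primary ICC: not given. Sample Size Selection attaches an unexplained p=0.10 to two continuous secondary endpoints. It may be an ICC, so 0.10 is included in the range.

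**1. The stated 93%.** Trial SE = sqrt(p(1-p)(1 + 199 x ICC)/1600), and power = Phi(0.12/SE - 1.96). With 21% fixed, power is about 100% at ICC 0. Exactly 93% needs ICC 0.039 (alternative variance), 0.047 (null and alternative variances) or 0.064 (log-ratio scale). At ICC 0.10 the same three formulas give 61%, 70% and 79%. The stated figure cannot be reproduced without an ICC; only the implied ICC can be found.

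**2. The scale.** Read literally, outcome minus 0.21 under a log link has intercept log(p - 0.21). That is log(0.12) = -2.12 at p = 0.33, and it is undefined at p of 0.21 or less. Intercept zero would mean p = 1.21. No difference from 21% is therefore not the null at intercept zero. The results below assume a model first put on a proper difference or log-ratio scale.

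**3. Error of the benchmark.** SE = sqrt(0.21 x 0.79/n). For n = 301 this is 0.0235, with 95% CI 0.21 +/- 1.96 x 0.0235 = 16.4% to 25.6%. For n = 201, 274 and 401 it is 0.0287, 0.0246 and 0.0203.

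**4. Effect on the interval.** SE with benchmark error = sqrt(trial SE² + benchmark SE²). Coverage of the reported interval = 2 x Phi(1.96/ratio) - 1. On the log-ratio scale the two variances are (0.67/0.33)(1 + 199 x ICC)/1600 and 0.79/(0.21 x n).

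| ICC | Trial SE at 33% | With benchmark error, n = 301 | Ratio, difference scale | Coverage (n = 201 to 401) | Ratio, log-ratio scale |
|---|---|---|---|---|---|
| 0.01 | 0.0203 | 0.0311 | 1.53 | 80% (74-83%) | 2.07 |
| 0.039 | 0.0348 | 0.0420 | 1.21 | 90% (87-91%) | 1.46 |
| 0.10 | 0.0537 | 0.0586 | 1.09 | 93% (92-93%) | 1.21 |

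Example at ICC 0.039: an observed 12-point effect is reported as 5.2 to 18.8 points; with benchmark error it is 3.8 to 20.2. The ratio 1.57 goes from 1.28-1.93 to 1.16-2.12.

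**5. False benefit if 21% is unbiased.** At a true rate of 21% and ICC 0.039 the trial SE is 0.0301. The ratio is sqrt(1 + 0.0235²/0.0301²) = 1.27, and P(Z > 1.96/1.27) is about 6.1% instead of 2.5%. At ICC 0.01 and 0.10 it is 12.0% and 4.0%. It returns to 2.5% if the true no-service rate lies below 21% by about 2.4 points (ICC 0.01), 1.6 (0.039; 1.2-2.3 for 401-201 controls) or 1.1 (0.10). As a small-sample check, a simulation at ICC 0.04 with a t test on 7 df gave two-sided error of about 10% with an estimated benchmark and 6% with a known one.

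**6. Power with benchmark error, same formulas as in step 1.**

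- Difference scale, alternative variance, ICC 0.0393: sqrt(0.0349² + 0.0235²) = 0.0421; Phi(0.12/0.0421 - 1.96) = 81%. With null and alternative variances, ICC 0.0470: 82%. Over 201-401 controls: 76-85%.
- Log-ratio scale, ICC 0.0635: sqrt(0.1315² + 0.0125) = 0.173; Phi(0.452/0.173 - 1.96) = about 74% (66-79%).
- ICC 0.01: about 97% on the difference scale. On the log-ratio scale, sqrt(0.0616² + 0.0125) = 0.128 gives about 94%.

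**The case against.** **A fixed reference rate is a recognised one-sample design.** An interval for the success rate against a declared goal of 21% would be valid. Aim 2, however, calls the 21% the probability expected without intervention and calls the result the intervention effect. Declaring it a fixed goal would change the question being answered.

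**21% may be conservative.** D-CLIP controls did receive services, so the direction is reasonable, and step 5 shows that a modest offset restores the false-benefit rate. This stands as far as it goes. It concerns bias, is not quantified, and does not supply the missing variance.

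**The planned effect survives.** In the ICC 0.039 example with 301 controls the corrected interval still excludes zero. A reader might infer that power is really 82%, but the documents do not support that. The figure rests on an ICC solved from exactly 93%, while the plan claims at least 93%, so a lower ICC and higher power are possible. Nor can a high ICC be used to dismiss the omission: at 0.10 the stated power would not hold.

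**An external comparator is foreseen.** The future-plans section mentions data from an observational cohort. That work is listed among additional analyses at study closeout that depend on separate funding, and it is not the primary analysis.

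**Sampling error may not be the largest uncertainty in the 21%.** This is fair. The D-CLIP results are described as unpublished, and the adjacent weight results are at eighteen months against a 3-year endpoint here. The power text, which refers to an effect "among the 2/3 of the study participants with prediabetes at baseline screening", implies about one third with diabetes, whom D-CLIP did not enrol. A reader might infer that 21% is biased for them. The documents fix neither direction nor size: Data Collection suggests that the HbA1c goal depends on baseline HbA1c, but the other two goals alone can give success.

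**Conclusion.** The point holds. The benchmark's variance is positive and independent of this trial's data, so an interval or p-value for the intervention effect that leaves it out is too narrow or too small at any ICC. That direction needs no assumption about the ICC or the control number. The size does: with 301 controls, coverage of a nominal 95% interval runs from about 80% at ICC 0.01 to 93% at ICC 0.10.

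Three limits apply. The error rates describe the analysis after it is put on a defined scale; a reader might take them as the error rate of the test exactly as written, but that test has no valid null. The two-sided rate of about 12% at ICC 0.039 (2 x 6.1%) counts false harm as well, so about 6% is the relevant figure for a claim of benefit, and only if 21% is unbiased. Finally, this covers sampling error alone, not whether 21% transfers to this population or to 3 years. The plan should be corrected, but the documents do not show that the trial would fail to detect the planned effect.

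**What to change.** - **Data Analysis, Aim 2.** Fit the unshifted success indicator with the planned log link and an offset of log(0.21), so that the exponentiated intercept is the ratio to 21%. For the primary interval and test, add 0.79/(0.21 x n) to the squared robust SE, where n is the number of D-CLIP controls analysed. State n. Report the difference as a secondary scale, with 0.21 x 0.79/n added to its variance.
- **Sample Size Selection.** Restate the primary power on the same log-ratio scale, with this variance and the assumed ICC, using one formula throughout.
- **Sensitivity analysis.** Prespecify a comparison of baseline-prediabetes participants with 21%, because D-CLIP enrolled only prediabetes. With two thirds of 1,600 = 1,067 completers (133 per site), difference-scale power at the ICCs in step 6 is about 80-81%, against about 92% with 21% fixed.

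The cost is wording, one added variance term and one figure from D-CLIP; no new data are collected. The downside is wider intervals and a less favourable stated power.

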When appropriate, all data analysis will be conducted for the entire study and individually by site. Qualitative data will be comprised of the translated, verbatim transcripts of the in-depth interviews and FGD. Textual data will be managed using the MAXqda10 (VERBI Software, 1989-2012). A codebook for each set of qualitative data will be created, tested for inter-coder reliability, and used to code the transcripts. When appropriate, qualitative data will be used to modify and improve intervention components and guide selection of adaptable components at each site. De-identified quantitative data will be entered into Microsoft Access databases. Range checks, disallowing invalid values, and adaptive double entry, along with regular data audits will ensure the accuracy of the electronic data. Data analysis will be conducted using SAS primarily. Descriptive analysis will be performed for all variables and outliers will be investigated for data errors. A probability of <0.05 will be considered statistically significant for all tests.

Aim 1: Success of program implementation will be assessed as follows:

- a) Program Adoption: Program adoption will be measured by quantifying participation in the program and success in reaching the goals of the lifestyle education program (weight loss, increased physical activity and diet improvements). Participation will be measured by calculating the percentages of total employees agreeing to screening, agreeing to participate in the program, and enrolling in lifestyle classes. Attendance records for study classes and other activities and numbers of diet/activity tracking booklets turned in for review by the health educator will be reviewed to determine percent attendance at each class and at classes overall. Physical activity [in Metabolic Equivalent of Task (METS)/day] will be quantified using the Global Physical Activity Questionnaire (GPAQ).⁹⁴ Diet changes will be quantified through a study-specific food frequency questionnaire, which will include food items that participants are encouraged to eat more or less often, as well as questions on diet-related behaviors (e.g., reading food labels, measuring portion sizes). A healthy diet score will be calculated from the food frequency questionnaire and other diet related questions.^{95,96} Changes in weight, BMI, waist circumference, physical activity, and diet score over time will

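### The primary GEE intercept test rests on 8 worksites with no few-cluster correction or reference distribution named; the usual uncorrected robust z test would run at about 11% two-sided instead of 5%

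*Combined protocol and SAP*

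**What the plan says.** Data Analysis, Aim 2, describes a GEE with a log link and binomial variance for the primary endpoint, which is reaching two or more risk-factor goals at three years, set against a fixed 21%. On clustering it says: "An exchangeable working correlation matrix will be used to incorporate the clustering within the 8 work-sites". All inference comes from one parameter. "The exponentiated point and interval estimates from the intercept of this model will quantify the intervention effect", and the p-value for the model's "intercept will provide a measure of the statistical significance of the findings". The method carries over: "A similar GEE approach will be used to estimate and test the significance of intervention effects on secondary endpoints".

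The paragraph names no variance estimator, small-sample correction, reference distribution or degrees of freedom for these tests. The one robust procedure it does name, "using a robust score test to assess the significance of", is for cross-product terms in the effect-modification analysis. The opening of Data Analysis sets the level: "A probability of <0.05 will be considered statistically significant for all tests". It does not say whether tests are one- or two-sided.

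Sample Size Selection plans "8 worksites with at least 250 eligible and enrolled participants per site and no more than 20% loss to follow-up" after three years and says this "will have 93% or more power to detect an estimated difference" of 33% against 21%. For a 30% reduction in diabetes incidence, among the two thirds of participants with prediabetes and from a baseline rate of 0.07 per year, it claims power close to 100%, with the other assumptions as for the primary endpoint. No ICC is printed for either endpoint. An undefined tag with the value 0.10 follows only the blood pressure and HbA1c statements.

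**The concern.** The trial has no control group, so the effectiveness claim rests on whether one intercept differs from a fixed constant. The standard error of that intercept is estimated from the scatter of 8 worksite results. The ordinary sandwich estimator is biased downward with so few clusters, and a normal reference ignores the error in estimating it. Both push the p-value down and narrow the interval. Enrolling more people per site does not help, because the shortage is of sites.

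A plan silent on this permits analyses whose actual two-sided error runs from about 4% to about 11%, with the choice left until the data are in hand. For power, the ICC is the input that matters most in a design with 8 large clusters, and without it a reader cannot tell whether the diabetes-incidence claim is secure.

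**Working it through.** **Inputs.** K = 8 sites. Analysed per site: 250 × 0.8 = 200, so 1,600 in all. Null 0.21, alternative 0.33. Level 0.05, taken as two-sided (my assumption). Equal sites are assumed throughout.

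**Type I error.** With equal sites the exchangeable GEE intercept is the mean of the 8 site means. On the identity scale the uncorrected sandwich variance divides the squared deviations of site means by K × K, where the usual variance of a mean uses K × (K − 1). The z statistic is therefore t₇ × √(8/7) = 1.069 × t₇.

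- Uncorrected, normal reference: P(|t₇| > 1.96/1.069) = P(|t₇| > 1.833) = 0.109. Upper tail alone: 0.055. Interval coverage: 1 − 0.109 = 0.891.
- Kauermann-Carroll (variance × 8/7) with t₇: 0.050.
- Mancl-DeRouen (standard error × 8/7 = 1.143) with t₇: P(|t₇| > 2.365 × 1.069) = 0.039.

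These rates do not depend on the ICC or on site size.

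As written, the dependent variable is the indicator minus 21%. It takes the values 0.79 and −0.21, which do not fit a log link with binomial variance. The log-scale check therefore used the 0/1 outcome with the intercept tested against log(0.21). Beta-binomial simulation with 200,000 runs per cell and ICC 0.005 to 0.06 gave 10.9–11.0% error and 88.9–89.2% coverage for the uncorrected test. Fitted log-link exchangeable GEEs (600 runs at each of two ICCs) gave 12.3% and 10.5%, with Monte Carlo standard error about 1.3 points. A continuous endpoint with identity link gave 11.0%.

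**Interval width against uncorrected.** Kauermann-Carroll: 2.365 × 1.069/1.96 = 1.29. Mancl-DeRouen: 2.365 × 1.143/1.96 = 1.38.

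**The stated 93%.** The design effect is 1 + 199 × ICC. At ICC 0, primary power is above 99.9%, so a computed 93% must include clustering. On the identity scale with variance at the alternative and a normal reference, ICC 0.0393 gives a design effect of 8.82. The standard error is √(0.33 × 0.67 × 8.82/1600) = 0.0349, and power is Φ(0.12/0.0349 − 1.96) = 0.93. The same solution under other conventions (identity or log scale, null or alternative variance) gives an ICC of 0.032 to 0.064 with a normal reference and 0.022 to 0.045 with t₇.

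**Diabetes incidence at the matching ICC.** n = 2000 × 2/3 × 0.8 = 1,067, or 133.3 per site; design effect 1 + 132.3 × ICC. Three-year risks are 1 − exp(−0.21) = 0.189 against 1 − exp(−0.147) = 0.137, or 0.21 against 0.147 on a linear reading. At ICC 0.0393 on the identity scale, the design effect is 6.20, the standard error is √(0.137 × 0.863 × 6.20/1067) = 0.0262, and power is Φ(0.0527/0.0262 − 1.96) = 0.52. Across conventions:

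| Variance | Scale | ICC giving 93%, normal / t₇ | Diabetes power at that ICC |
|---|---|---|---|
| Alternative | Identity | 0.039 / 0.027 | 52–65% |
| Alternative | Log | 0.064 / 0.045 | 28–36% |
| Null | Identity | 0.054 / 0.038 | 34–43% |
| Null | Log | 0.032 / 0.022 | 61–75% |

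**Power at assumed ICCs** (variance at the alternative; ranges over scale and, for diabetes, risk form):

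| ICC | Primary, normal / t₇ | Diabetes, normal / t₇ |
|---|---|---|
| 0 | ~100% / ~100% | 99–100% / 95–99.8% |
| 0.001 | ~100% / ~100% | 98–100% / 93–99.6% |
| 0.01 | ~100% / 99.9–100% | 79–97% / 67–90% |
| 0.02 | 99.6–100% / 97–99.8% | 60–86% / 48–74% |
| 0.04 | 93–99% / 83–95% | 39–64% / 31–52% |
| 0.06 | 81–94% / 68–86% | 29–49% / 23–39% |

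**The case against.** The plan is silent, and silence is not a choice of the uncorrected test. A reader might infer that the trial will run at 11%. The documents do not support that, because a competent analyst could still apply a correction. What stands is that nothing commits the analyst to one. A robust score test on the intercept would also hold the level (3.9%), but the plan names that test only for effect modification, and it would not by itself repair the Wald interval.

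A reader might also take 11% as the rate of false claims of benefit. It is the two-sided rate. In the direction of benefit it is 5.5% against 2.5%, or 8.4% against 5% if a one-sided 0.05 test were meant.

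On power, a reader might infer that the two figures contradict each other, or that 93% is wrong. Neither follows. The primary figure is worded as a minimum, so it may be a floor. The carried-over assumptions may be only the number of sites, the site size and the dropout, and ICCs commonly differ between endpoints. Holding the between-site coefficient of variation constant instead of the ICC gives diabetes power of 57–93%. The mismatch therefore depends on 93% being the computed value and on one common ICC.

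The tag with 0.10 could be a garbled correlation. It is attached to two other endpoints, and an ICC of 0.10 would put primary power at 53–79% with a normal reference, so it cannot be the value behind 93%.

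**Conclusion.** The concern holds as an omission with a conditional size. The method for the primary and secondary GEE tests is incomplete where 8 clusters make it matter. Under the default uncorrected robust z test with roughly equal sites, the two-sided level is about 11% instead of 5%, and 95% intervals cover about 89%. This does not rest on any ICC. It does rest on near-equal sites and on reading the model as a 0/1 outcome tested against log(0.21).

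The power point is supporting and is not an arithmetic error. The two ICCs are unstated and neither figure is shown to be wrong. If 93% is the computed value, one common ICC of about 0.02 to 0.06 leaves diabetes-incidence power at about 28–75%. If 93% is a floor, or the ICCs differ, both statements can hold, but power close to 100% for diabetes incidence needs an ICC close to zero. The design itself is not undermined; the point should be fixed before analysis.

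**What to change.** In Data Analysis, Aim 2, pre-specify one few-cluster method for all primary and secondary GEE tests and intervals. Kauermann-Carroll with t on 7 degrees of freedom holds about 5%, and Mancl-DeRouen with the same reference about 4%. Which to use is the study statistician's choice; what matters is naming it in advance. State that tests are two-sided, if so intended, and write the primary null as the intercept equal to log(0.21) for the 0/1 outcome. The Cox model under consideration for diabetes incidence would need its own statement on clustering.

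In Sample Size Selection, give the ICC or ICC range used for each endpoint with its source, and restate the primary and diabetes-incidence powers from it with t on 7 degrees of freedom. I propose no replacement power, because the documents give no ICC for these endpoints.

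The cost is a few sentences and one recalculation. Intervals will be about 29% (Kauermann-Carroll) or 38% (Mancl-DeRouen) wider than uncorrected ones. Restated powers will be lower if the present ones used a normal reference: for the primary endpoint, from 99.6–100% to 97–99.8% at ICC 0.02, and from 93–99% to 83–95% at 0.04. No further participants, sites or data are needed.
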